3.1.2 Rationale of Study Design

This double-blind, placebo-controlled study is designed to evaluate the efficacy, safety, tolerability, PK, and PD of SKI-O-703 in persistent and chronic ITP patients. The results of this study will guide on further clinical evaluation of SKI-O-703 patients with ITP. The double-blind placebo-controlled design has been selected to minimize bias in the evaluation of the safety, efficacy, PK, and PD.

Since the 400 mg BID dose level has not been investigated in healthy volunteer studies, a safety run-in group will be implemented. To protect the study blind, 5 subjects will be included in the safety run-in period to reflect the overall 2:2:1 randomization, resulting in 2 subjects each being dosed at 400 mg and 200 mg BID and 1 subject being dosed with placebo. An interim safety and PK data review will be performed by the DMC once the subjects in the safety run-in period complete their Day 8 (± 2 days) assessments. Further

enrollment in each treatment group will only resume after safety and PK data of the first week for the first 5 subjects are reviewed and considered satisfactory by the DMC.

Serial blood samples (5 mL) for PK assessment of SKI-O-592 and its metabolites (M2 and M4) from all subjects in the PK/PD subset will be obtained from this study, which in turn would help refine the sparse sampling approaches needed for later Phase 3 studies leading to a better population PK analysis in Phase 3.

The power of a statistical test is typically a function of the magnitude of the treatment effect, the designated Type I error rate (α , risk of false-positive result) and the sample size (n). When designing a trial, it is important to decide upon the desired study power (typically 80% for a Phase 2 study) and calculate the necessary sample size to achieve this goal. Since it is often not feasible to conduct large trials during early stage of development, it is necessary to identify the strategies to optimize the statistical power of smaller studies.

In this study, platelet response, defined as platelet count $\geq 30,000/\mu\text{L}$ and doubling the baseline (average of 2 previous counts), at any visit during the treatment period and without use of rescue medication, is selected as the primary endpoint.

4 Subject Selection and Withdrawal Criteria

4.1 Selection of Study Population

A minimum of 60 subjects will be enrolled at multiple sites in Korea, US, and EU. Subjects will be assigned to study drug only if they meet all of the inclusion criteria and none of the exclusion criteria. Deviations from the inclusion and exclusion criteria are not allowed because they can potentially jeopardize the scientific integrity of the study, regulatory acceptability, or patient safety. Therefore, adherence to the criteria as specified in the protocol is essential.

4.1.1 Inclusion Criteria

Each subject must meet all of the following criteria to be enrolled in this study:

1. Able to provide written informed consent and agreeable to the schedule of assessments
2. Male or female subjects, aged 18 years or older (or ≥ 19 years of age for Korean subjects per local regulations)
3. Diagnosis of primary ITP (persistent or chronic) made according to the American Society of Hematology 2011 evidence-based guideline
4. Failed to respond or relapsed after at least 1 prior therapy (eg, corticosteroids, IVIG, anti-D, rituximab, TPO-receptor agonists, splenectomy, and immunosuppressants such as vincristine, mycophenolate mofetil, and azathioprine), with a platelet count of $<30,000/\mu\text{L}$ on 2 occasions at least 7 days apart with the confirmatory count being taken during Screening (the most recent result from the central laboratory will be considered as the confirmatory platelet count, when an unscheduled visit(s) is performed during the screening period). Response to such prior therapy is defined as platelet count of $\geq 30,000/\mu\text{L}$ and >2 times increase from baseline in the absence of bleeding. Failure to respond and relapse to such prior therapy are defined as failure to achieve and/or failure to maintain response on a tolerable regimen of prior therapy.
5. Adequate hematologic, hepatic, and renal function (absolute neutrophil count $\geq 1.5 \times 10^9/\text{L}$, hemoglobin [Hgb] $\geq 10.0 \text{ g/dL}$, aspartate aminotransferase [AST] and alanine aminotransferase [ALT] $\leq 2.0 \times \text{ULN}$, bilirubin $\leq 1.5 \times \text{ULN}$, albumin $\geq 3 \text{ g/dL}$, estimated glomerular filtration rate [eGFR] $\geq 40 \text{ mL/min/1.73m}^2$, and creatinine $\leq 1.5 \times \text{ULN}$)

6. ECOG performance status of 0, 1, or 2
7. Both male and female subjects must agree to take the following steps to reduce the potential for transmission of genetic material containing the investigational product:
 - a. Both male and female subjects, the subject and their partners of childbearing potential must agree to use 2 of the following medically acceptable methods of contraception from the time of randomization, during the study, and for 6 months following discontinuation of study drug, of which:
 - o One must be a highly reliable method of contraception, such as:
 - An intrauterine device or intrauterine system implanted for at least 30 days prior to Day 1
 - Surgical sterilization of one of the partners for at least 6 months prior to the date of informed consent (assuming this will be the only partner for the whole duration of the clinical trial)
 - Consistent and correct use of hormonal contraceptives (hormonal implants, injectables, contraception pills, transdermal patches, or contraceptive rings) for at least 30 days prior to Day 1
 - o One supplementary barrier method, such as:
 - Male or female condom always with spermicide (a spermicidal foam/gel/film/cream)
 - Diaphragm or cervical/vault caps always with spermicide (a spermicidal foam/gel/film/cream)
 - Double-barrier methods (which means a barrier method used by both partners at the same time), even when used with spermicide, are not considered to be highly reliable contraception methods, and as such, may not be the only forms of contraception used
 - b. Female subjects must agree not to breastfeed starting from the time of Screening, throughout the study, and until after 6 months following the last dose of study drug.

- c. Male subjects must agree not to donate sperm starting from the time of randomization, throughout the study, and until after 6 months following the last dose of study drug
- d. For subjects and partners considered not of childbearing potential, the following conditions apply:
 - a. Menopausal females must have experienced their last period more than 12 months prior to the date of informed consent to be classified as not of childbearing potential.
 - b. Male and female subjects are in a situation of abstinence from heterosexual intercourse from Screening until after 6 months following the last dose of study drug when this is in line with the preferred lifestyle of the subject (eg, homosexual women and men or a member of a religious order such as nuns and priests).

4.1.2 Exclusion Criteria

Subjects meeting any of the following criteria will be excluded from the study:

- 1. History of any clinically significant disease or disorder that in the opinion of the investigator or the sponsor may put the subject at risk due to study participation, impact the subject's ability to participate in the study, or influence the study results
- 2. History of current, active malignancy requiring or likely to require chemotherapeutic or surgical treatment during the study, with the exception of non-melanoma skin cancer, carcinoma in situ of the cervix, and localized prostate cancer managed by active surveillance
- 3. Transfusion with blood or blood products or plasmapheresis within 2 weeks before the first administration of study drug (Day 1)
- 4. PT INR > 1.5
- 5. History of known inherited coagulopathy (including prothrombotic conditions such as Factor V Leiden, APC resistance, AT-III deficiency, and lupus anticoagulant), or recent arterial or deep venous thrombosis within the preceding 6 months

6. Change in corticosteroid or immunosuppressant (azathioprine, mycophenolate mofetil, cyclosporine) dose within 2 weeks prior to Day 1 (more than 10% variation from Day 1 daily doses)
7. Treatment with thrombopoietin (TPO) receptor agonists within 2 weeks before Day 1
8. Treatment with rituximab or splenectomy within the 8 weeks prior to Day 1
9. Treatment with IVIGs within 4 weeks prior to Day 1
10. Infections requiring intravenous antibiotics or hospitalization within 3 months prior to Day 1
11. Subject had positive test results at Screening for human immunodeficiency virus, hepatitis B surface antigen (HBsAg), or hepatitis C virus antibody. Subjects with past or resolved hepatitis B infection (defined as having a negative HBsAg test and a positive IgG antibody to hepatitis B core antigen [anti-HBc]) are eligible but hepatitis B virus (HBV) DNA must be obtained in these subject prior to Cycle 1, Day 1, and must demonstrate no active infection. Subjects positive for hepatitis C virus (HCV) antibody are eligible only if polymerase chain reaction (PCR) is negative for HCV RNA.
12. Live vaccine within 28 days prior to Day 1 or plan to receive one during the study
13. History or presence of any gastrointestinal, hepatic, or renal disease or any other condition known to interfere with the absorption, distribution, metabolism, or excretion of drugs
14. Subject has not recovered from a recent medical/surgical procedure or trauma by Day 1 as determined by the investigator
15. Uncontrolled hypertension (as defined by systolic blood pressure ≥ 160 mmHg or diastolic blood pressure ≥ 100 mmHg)
16. Subject had ECG findings of corrected QT interval by Fridericia formula (QTcF) > 480 msec, cardiac arrhythmias, or clinically significant cardiac or ECG abnormalities
17. Subject have received any investigational medication within 30 days or 5 half-lives prior to Day 1, whichever was longer

18. Concomitant use of any anticoagulants and platelet aggregation inhibiting drugs including aspirin (within 14 days of planned dosing through end of follow-up)
19. Female subject who is currently pregnant or breastfeeding
20. Prior treatment with a SYK inhibitor
21. Planned surgery in the time frame of the dosing period.

4.2 Withdrawal of Subjects From Study Drug and/or the Study

The duration of the study is defined for each subject as the date signed informed consent is provided through date of the last follow-up visit on Week 16.

4.2.1 Reasons for Withdrawal/Discontinuation

Subjects may withdraw from the study at any time and for any reason without prejudice to their future medical care by the investigator or at the study site. Every effort should be made to keep subjects in the study. The reasons for subjects not completing the study will be recorded. A subject may be withdrawn from the study for any of the following reasons:

1. Noncompliance with the protocol
2. A serious or intolerable adverse event(s) (AE[s]) that in the investigator's opinion requires withdrawal from the study
3. Central nervous system bleeding or life-threatening gastro-intestinal bleeding. Please also refer to the additional information in the 'Note' at the bottom of this section.
4. Laboratory safety results that reveal clinically significant hematological or biochemical changes from the baseline values
5. Symptoms of an intercurrent illness not consistent with the protocol requirements or that justify withdrawal
6. Lost to follow-up. Subjects that are considered lost to follow-up, reasonable attempts must be made to obtain information on the final status of the subject. At a minimum, 2 phone calls must be made and 1 certified letter must be sent for documentation
7. Other reasons (eg, pregnancy, development of contraindications of use of study drug, breakthrough bleeding)

8. The subject withdraws consent or the investigator or sponsor decides to discontinue the subject's participation in the study
9. Death of the subject.

Note: Bleeding events in the ITP studies are common during the first few weeks of the study before the drug has a chance to take effect; hence, all the bleeding events in this study should be recorded as an AE or SAE (based on seriousness criteria). These events should not result in removal of the subjects from the study, at least during the first 4 weeks of treatment. As the standard of care among the participating countries may differ, platelet transfusions are allowed as a rescue therapy for such events; however, these therapies may be reserved for serious or life-threatening bleeding events.

The investigator will also withdraw a subject if Oscotec Inc. terminates the study. Upon occurrence of a serious or intolerable AE, the investigator will confer with the sponsor. If a subject is discontinued because of an AE, the event will be followed until it is resolved. Any subject may withdraw his or her consent at any time. Although Oscotec Inc. has every intention of completing the study, Oscotec Inc. reserves the right to discontinue the study at any time for clinical or administrative reasons, please refer to [Section 11.3](#) for further details.

4.2.2 Handling of Withdrawals

Subjects are free to withdraw from the study or study drug at any time upon request. Subject participation in the study may be stopped at any time at the discretion of the investigator or at the request of the sponsor.

Subjects who discontinue study drug or active participation in the study will no longer receive study drug. When a subject withdraws from the study drug or active participation in the study, the reason(s) for withdrawal shall be recorded by the investigator on the relevant page of the electronic case report form (eCRF). Whenever possible, all subjects who discontinue study drug permanently or withdraw from the study prematurely will undergo all end-of-study assessments. Subjects who fail to return for final assessments will be contacted by the site in an attempt to have them comply with the protocol. Following a minimum of 2 documented unsuccessful telephone calls, a registered letter will be sent to the subject in a final attempt to ensure protocol compliance.

It is vital to obtain follow-up data on any subject withdrawn because of an AE or SAE. In every case, efforts must be made to undertake protocol-specified safety follow-up procedures.

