1.4 Placebo Rationale

The proposed study is a double-blind, placebo-controlled, randomized trial of two doses of oral SKI-O-703 for patients with persistent and chronic ITP. Subjects will be allowed to receive stable doses of background medications including corticosteroids and immunosuppressive drugs, in line with the current standard of care. Any subject who cannot adhere to the protocol or who discontinues treatment will have an end-of-treatment visit and will be followed for the intended duration of the study.

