6.1 Study Visits

The total study duration will be 20 weeks per subject, which consists of up to 4 weeks of screening period. The treatment period will be 12 weeks (split into 1-week safety run-in period and 11-week treatment period for the first 5 subjects). The post-treatment follow-up period will be of 4 weeks. Each assessment will be carried out at timepoints indicated in the Schedule of Events table and clarified in the footnotes presented below the table. The schedule of events is summarized in [Table 2](#).

Table 2 Schedule of Events

	Screening (D-28 to D-1)	On-treatment Visits					Follow-up Clinic Visits	Early Withdrawal/ Unscheduled visit
		W1 (D1), W5 and 9 (± 3 days)	W1D4 (± 1 day)	W2D8 (± 2 days)	W3, 7, 11 (± 3 days)	W12 (D84 or D85) (EOT) (± 3 days)	End of Study W16 (± 1 week)	
Clinic visits	X	X ^a		X ^{a*}	X ^a	X ^a	X ^a	X
Informed consent	X							
Inclusion/Exclusion criteria	X	X ^h						
AEs		<----->						X
Concomitant medications	X	X		X*	X	X	X	X
Height	X							
Weight	X	X		X*		X	X	X
Physical examination/medical history ^b	X	X		X*	X	X	X	X
ECG ^c	X	X		X		X	X	X
Vital signs	X	X		X*	X	X	X	X
Urinalysis	X	X		X*	X	X	X	X
Hep B & C, HIV, HBV DNA, HCV RNA	X							
Pregnancy test/ FSH ^d	X	X				X	X	X
Contraception status	X	X		X*		X	X	X
ABO and Rh blood type	X							
Serum chemistry	X	X		X*	X	X	X	X
Hematology, differential	X	X	X ^{a,e}	X ^{a,e}	X	X	X	X
PT/INR PTT	X					X		
Study drug dispensing		X			X			X ^f
Study drug administration		X	X	X*	X	X		X ^f
Blood samples for PK and PD assessments ^g		X ^h		X*		X		

	Screening (D-28 to D-1)	On-treatment Visits					Follow-up Clinic Visits End of Study W16 (± 1 week)	Early Withdrawal/ Unscheduled visit
		W1 (D1), W5 and 9 (± 3 days)	W1D4 (± 1 day)	W2D8 (± 2 days)	W3, 7, 11 (± 3 days)	W12 (D84 or D85) (EOT) (± 3 days)		
Bleeding Score ⁱ		X		X*		X	X	X
Quality of life using SF-36 score		X				X	X	X
Pharmacogenomic screening		X ^j						

Abbreviations: AEs, adverse events; D, Day; ECG, 12-lead electrocardiogram; EOT, end-of-treatment; FSH, follicle stimulating hormone; HBV, hepatitis B virus; HCV, hepatitis C virus; hep, hepatitis; HIV, human immunodeficiency virus; PD, pharmacodynamics; PK, pharmacokinetics; PT/INR, prothrombin time/international normalized ratio; PTT, partial thromboplastin time; W, Week

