- * Subjects in the safety run-in period will have clinic visit on Week 2/Day 8 (± 2 days) for the mentioned assessments including hematology (differential) tests. For other subjects, this visit will be laboratory only visit to perform hematology (differential) tests only.
- a Clinic / laboratory visit windows are about ± 3 days for all dosing period and laboratory visits and about ± 1 week for clinic follow-up visits. The W12/D84 or D85 (EOT) visit should be performed while on therapy.
- b Complete physical examination at Screening and abbreviated physical examination at other visits.
- c For all subjects: predose ECG on the first day of dosing and on Day 1 of each subsequent week as specified in the table above. For subjects in the safety run-in subsets and PK/PD subset who are in safety run-in subset only: ECG on the first day of dosing at predose, 1, 2, 4, 8, and 12 hours (± 10 min) after the study drug administration.
- d For women of childbearing potential only: Serum pregnancy tests are performed at Screening. To confirm pregnancy, urine pregnancy test will be performed locally on Day 1 prior to randomization and prior to study drug administration on clinic visit days at mentioned timepoints. If urine pregnancy test is negative, dosing will be started; if urine pregnancy test is positive then with-hold dosing and perform a serum pregnancy test. FSH testing is needed at Screening for post-menopausal female subjects only.
- e Laboratory only visits will be performed on Day 4 ± 1 day (Week 1) for all subjects and on Week 2/Day 8 (± 2 days) for subjects other than those enrolled in the safety run-in period.
- f Study drug dispensing and administration can occur at unscheduled visit.
- g Samples to be collected as follows:

For the subjects in the safety run-in period only (for PK only; no PD assessments):

- Day 1: morning predose, 0.25 (± 5 min), 0.5 (± 5 min), 1, 2, 4, 8, and 12 hours (± 10 min) (evening predose).
- Day 8 (± 2 days): morning predose, 0.25 (± 5 min), 0.5 (± 5 min), 1, 2, 4, 8, and 12 hours (± 10 min) (evening predose).
- Week 12: morning predose, 0.25 (± 5 min), 0.5 (± 5 min), 1, 2, 4, 8, and 12 hours (± 10 min).

For the subjects in the PK/PD subset only (for PK/PD):

- Day 1: morning predose, 0.25 (± 5 min), 0.5 (± 5 min), 1, 2, 4, 8, and 12 hours (± 10 min) (evening predose).
- Week 12: morning predose, 0.25 (± 5 min), 0.5 (± 5 min), 1, 2, 4, 8, and 12 hours (± 10 min).

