#### *Sensitivity analysis based on treatment-policy strategy:*

The primary analysis will be repeated on assessments in all scheduled visits from post-baseline until Week 12, regardless of patients using rescue medication or discontinuation. The missing platelet count values will be imputed by Multiple Imputation (MI) method for all treatment groups, under the missing at random (MAR) framework.

The SAS procedure MI will be used to impute missing platelet count at the scheduled analysis visits (up to Week 12) to create 25 complete data sets. The missing data patterns

will be checked by treatment and at the scheduled visits for the platelet count. If there are non-monotone missing patterns, two separate imputation procedures will be used to complete the imputation process.

In the first step, the Markov Chain Monte Carlo (MCMC) method will be used to impute missing values by treatment to create 25 imputed data sets with monotone missing patterns. The seed will be set to 7032101, the imputed values will be rounded to 3 decimals with  $10^9/L$  unit and a single chain will be used to produce imputations.

In the second step, the monotone regression method will be used to impute the remaining missing values for the 25 data sets with monotone missing patterns. The MONOTONE REG statement will be used with seed 2101703. The missing values at each visit will be imputed based on treatment, values at baseline and previous visits, and prior TPO-receptor agonist use.

If model fail to converge because the number of visits is more than number of subjects, the model will be reformed. The nearest visits (Week 1 Day 1 to Week 2 Day 8, Week 3 to Week 7, and Week 9 to Week 12) will be imputed by two steps imputation procedures described above separately with unique seed. For visits Week 1 Day 1 to Week 2 Day 8, the seed used in first step is 7032101 and in second step is 2101703. For visits Week 3 to Week 7, the seed used in first step is 1021984 and in second step is 1984102. For visits Week 9 to Week 12, the seed used in first step is 1072018 and in second step is 2018107.

After the completion of two steps imputations, the response will be defined based on platelet counts in the 25 complete datasets and the same logistic regression model described in [Section 8.1.1](#) will be used to analyze the 25 complete datasets. The SAS procedure MIANALYZE will be used to combine the results for the statistical inferences.

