### 8.2.2. Change from Baseline in Platelet Counts

#### *Primary Analysis*

The primary Analysis will be performed on all observed data until Week 12, regardless of rescue medication and discontinuation.

Change from baseline in the average of the last 2 platelet counts will be analyzed using an analysis of covariance (ANCOVA) model with covariates including baseline platelets count, treatment, rescue medication use, and prior TPO-receptor agonist use.

The within-group least-square (LS) means, the associate standard errors (SE), and the treatment differences in LS means, the associated SE, 95% CIs and p-values will be derived from the model to compare each active treatment group against placebo.

Descriptive statistics of baseline value, observed value and change from baseline will be presented by treatment group.

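### The protocol gives two accounts of follow-up after study drug is stopped, and the SAP's treatment-policy sensitivity analyses depend on the one that the withdrawal section and visit schedule do not carry

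*Protocol*

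**What the plan says.** **Protocol 1.4 (Placebo Rationale).** The rule here covers a non-adherent subject, or one who "discontinues treatment will have an end-of-treatment visit and will be followed for the intended duration of the study".

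**Protocol 4.2.2 (Handling of Withdrawals).** Stopping drug and leaving the study fall under a single rule. Whenever possible, "all subjects who discontinue study drug permanently or withdraw from the study prematurely will undergo all end-of-study assessments". The next step treats this as the last contact: "Subjects who fail to return for final assessments will be contacted by the site".

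**Protocol 6.1, Table 2.** The only column for early stoppers is "Early Withdrawal/ Unscheduled visit". Hematology is marked there. No text says that the on-treatment columns continue after drug is stopped, and footnote a adds: "The W12/D84 or D85 (EOT) visit should be performed while on therapy".

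**SAP 8.1.2, treatment-policy sensitivity analysis of the primary endpoint.** It takes all scheduled visits to Week 12, "regardless of patients using rescue medication or discontinuation". For gaps: "The missing platelet count values will be imputed by Multiple Imputation (MI) method for all treatment groups, under the missing at random (MAR) framework". SAP 8.2.2 repeats this method for change from baseline.

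**SAP 8.2.2, main analysis of change from baseline.** "The primary Analysis will be performed on all observed data until Week 12, regardless of rescue medication and discontinuation". No imputation is stated.

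**The concern.** A treatment-policy analysis asks what happened to everyone randomized, including after they stopped drug. It needs platelet counts from that period. Protocol 1.4 promises the follow-up that would supply them, but the promise appears only in a rationale section. The withdrawal section and the schedule, which are the operational text for sites, do not repeat it.

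If sites follow 4.2.2 and Table 2, most off-drug counts are never taken, and no later SAP edit can recover them. The two treatment-policy analyses would then carry a name that does not match what they estimate. In the main ANCOVA of 8.2.2, an early stopper's last two counts would be mostly on-drug values from the first weeks. With planned arms of 24, 24 and 12, and dosed dropouts not replaced (Protocol 4.2.3), a few stoppers per arm are enough to matter.

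**Working it through.** **1. The plan's own figure.** Protocol 7.4 assumes 50% response on active drug (n = 24) and 1% on placebo (n = 12), with 82.7% power (82.74% in SAP 4.4). A pooled-variance normal approximation with continuity correction reproduces it:

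- pooled rate = (24 × 0.50 + 12 × 0.01)/36 = 0.3367
- null SE = √[0.3367 × 0.6633 × (1/24 + 1/12)] = 0.1671
- alternative SE = √(0.50 × 0.50/24 + 0.01 × 0.99/12) = 0.1060
- correction = 0.5 × (1/24 + 1/12) = 0.0625
- power = Φ[(0.49 − 0.0625 − 1.96 × 0.1671)/0.1060] = 82.7%

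This point does not affect that figure. The 50% and 1% rates are reused in step 5.

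**2. The two accounts side by side.**

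| | Protocol 1.4 | Protocol 4.2.2 and Table 2 |
|---|---|---|
| Who | Subjects who stop treatment | Subjects who stop drug or leave the study, treated alike |
| Visit | End of treatment | End-of-study assessments; one early-withdrawal column |
| Afterwards | Followed for the intended duration | No off-drug visits described |

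End of treatment (Week 12) and end of study (Week 16) are different columns in Table 2. PT/INR and PTT, for example, are marked at Week 12 but not at Week 16. So the accounts differ on the visit as well as on what follows it.

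**3. How many counts would be missing.** Table 2 schedules eight post-baseline counts in the treatment period: Day 4, Day 8 and Weeks 3, 5, 7, 9, 11 and 12. A subject who stops after Week 3 has five of the eight outstanding. Under 4.2.2 and Table 2, about one further count is likely. SAP 4.3 assigns no visit windows and uses the CRF visit name, so that count may not map to any scheduled visit.

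**4. What the imputation would use.** In SAP 8.1.2 the first step imputes by treatment. The second uses treatment, baseline, earlier visits and prior TPO-receptor agonist use. Neither step has a term for being on or off drug. With few off-drug counts, the later values of an active-arm stopper are predicted mostly from active-arm patients still taking drug.

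**5. Illustrative size, one active arm.** The endpoint is response at any visit, so only subjects who stop before responding matter. Let d be their share of the arm, p_on the on-drug rate (0.50, from the plan) and p_off their true off-drug rate. Neither d nor p_off is in the documents; both are assumed. As a simplification, stoppers are imputed at p_on.

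- True treatment-policy rate = p_on × (1 − d) + p_off × d
- Overstatement = d × (p_on − p_off)

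| d (subjects of 24) | p_off = 1% | p_off = 25% |
|---|---|---|
| 10% (2.4) | true 45.1%, +4.9 points | true 47.5%, +2.5 points |
| 20% (4.8) | true 40.2%, +9.8 points | true 45.0%, +5.0 points |
| 30% (7.2) | true 35.3%, +14.7 points | true 42.5%, +7.5 points |

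If the off-drug rate equaled the on-drug rate, the overstatement would be zero.

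**6. What the table does not show.** It covers one active arm, not the contrast. Under an any-visit endpoint, each imputed visit is another chance to cross the threshold, in the placebo arm as well. Placebo could therefore be inflated too.

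**The case against.** The protocol passages can be read together. Section 4.2.2 gives no timing, Table 2 labels Week 16 as end of study, 4.2.1 asks for every effort to keep subjects in the study, and SAP 5.1 tabulates stopping treatment separately from leaving the study. On that reading a stopper has an end-of-treatment visit and continues to Week 16. The reading is possible, but no visit schedule supports it and 4.2.2 does not state it, so the need to reconcile stands.

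Several stronger readings are tempting, and the documents do not support them:

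- **That there would be no off-drug counts at all.** Hematology is marked in the early-withdrawal column, and footnote a does not forbid off-drug counts.
- **That the main efficacy result treats dropouts as still on drug.** SAP 8.1.1 counts a subject whose response cannot be adequately determined as a non-responder.
- **That every analysis made regardless of discontinuation imputes.** The main ANCOVA in 8.2.2 uses observed data and carries nothing forward. The last two counts in the treatment period are what its endpoint definition asks for.
- **That the plan never departs from own-arm imputation.** The missing-not-at-random analysis in 8.2.2 already imputes from placebo, though only for change from baseline under a hypothetical strategy.
- **That safety follow-up of stoppers is lost.** Section 4.2.2 calls follow-up data after an AE withdrawal vital, 4.2.1 follows an AE that led to discontinuation until it resolves, and 6.4.5.3 collects AEs to Week 16.
- **That the discontinuation events in Table 1 must be commoner on active drug.** Its footnote presents them as examples from agents with a similar mechanism. Protocol 1.1 reports no apparent treatment- or dose-related trends in laboratory or ECG results in the multiple-dose study, and no significant blood-pressure changes versus placebo.

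**Conclusion.** The point holds in limited form and should be fixed, though it does not undermine the primary analysis. Protocol 1.4 disagrees with 4.2.2 and Table 2 on what happens after drug is stopped. If sites follow the latter, the treatment-policy sensitivity analyses of the primary endpoint and of change from baseline would be closer to hypothetical estimates, in which dropouts stayed on drug.

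The size is unknown. The illustration of about 2.5 to 15 points in an active arm rests on an assumed 10–30% stopping before response, an assumed off-drug rate of 1–25%, and imputation at the planned 50%. A reader might infer that the comparison with placebo is biased toward the drug by that amount. That is not established, because the placebo arm may be inflated as well.

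**What to change.** **Protocol 4.2.2.** Reconcile it with 1.4 by stating two cases for data collection:

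1. Subjects who stop study drug only: the end-of-treatment assessments, then the remaining scheduled visits through Week 16. At a minimum these collect hematology, concomitant and rescue medication, AEs, and the bleeding score where scheduled.
2. Subjects who withdraw from the study: the early-withdrawal visit.

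**Protocol Table 2.** Add a footnote that the scheduled visits, apart from dosing and PK/PD sampling, continue after study drug is stopped. Limit the on-therapy condition in footnote a to subjects still on drug.

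**SAP 8.1.2 and the matching treatment-policy analysis in 8.2.2.** Use the observed off-drug counts. For counts still missing after discontinuation, add a placebo-based imputation like the one already specified in 8.2.2. Imputing from each arm's own off-drug observations is not a sound default: in the illustration an active arm has only about 2 to 7 stoppers.

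**Cost.** Subjects off drug keep attending visits, but none beyond the follow-up that 1.4 already promises. The rest is protocol wording, a footnote and modest extra SAP programming.
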